6.3.2 Fulvestrant toxicity management

6.3.2.1 Management of Hepatic Impairment

A Fulvestrant dose of 250 mg is recommended for patients with moderate hepatic impairment (Child-Pugh class B) to be administered IM into the buttock slowly (1 - 2 minutes) as one 5 mL injection on Day 1 and Day 15 of the first and Day 1 of each subsequent 28-day cycle. Fulvestrant has not been evaluated in patients with severe hepatic impairment (Child-Pugh class C).

6.3.3 Other toxicities

Other toxicities that are not clearly attributable to copanlisib or fulvestrant, including overlapping toxicities, should be initially managed as follows:

- Treatment interruption or dose modification for Grade 1 or grade 2 AEs per CTCAE would be implemented at the investigator and patient's discretion.
- Both agents should be interrupted for Grade 3 AEs per CTCAE until the AEs have reached grade 1 or have returned to baseline. Following the resolution of toxicity, copanlisib may be resumed at the same dose level or at one or more dose levels lower, at the investigator's discretion. Fulvestrant should be resumed at the same dose level. Sequential reintroduction of each agent should be considered if clinically appropriate.
- Both agents should be interrupted for Grade 4 AEs per CTCAE until the AEs have reached grade 1 or have returned to baseline. For AEs that are not life-threatening and that can

Proprietary Information of MD Anderson

Protocol 2020-1241

19 October 2022

be managed, treatment with copanlisib may be resumed at a lower dose level, but fulvestrant should be resumed at the same dose level. Otherwise, patients must discontinue treatment. Sequential reintroduction of each agent should be considered if clinically appropriate.

6.3.4 COVID-19/SARS-CoV-2 Infection

The following guidelines apply to patients with confirmed (positive by regulatory authority-approved test) or presumed (test pending/clinical suspicion) coronavirus disease 2019 (COVID-19)/severe acute respiratory syndrome coronavirus 2 (SARS-CoV-2) infection:

- For patients with active SARS-CoV-2 infection, study treatment should be delayed for at least 14 days from the first positive COVID-19 test or start of symptoms, whichever is later.
- Prior to restarting study treatment, patients should be afebrile for 72 hours and SARS-CoV-2-related symptoms should have recovered to Grade ≤ 1 for a minimum of 72 hours. The sponsor should be informed when study treatment is resumed.

The sponsor and/or the supporting company must be informed within 24 hours of awareness of a patient with COVID-19/ SARS-CoV-2 infection.

6.4 Concomitant Therapy

All medications that the investigator considers necessary for a patient's welfare may be administered at the discretion of the investigator in keeping with the community standards of medical care. All concomitant medication received within 28 days before the first dose of study treatment and 30 days after the last dose of study treatment -including all prescription, over-the-counter, IV medications and fluids, supportive care drugs and the drugs used to treat AEs or chronic diseases, and non-drug supportive interventions- will be captured in the electronic medical record (EMR), but not in the electronic case report forms (eCRF).

6.4.1 Prohibited Medications/Therapies

Use of the following concomitant medications/therapies is prohibited during the study:

- Any chemotherapy, radiation therapy, immunotherapy, hormone, or biologic therapy for cancer treatment other than that under investigation in this study.
Exceptions include the following:
 - Palliative radiotherapy is allowed during the study if the patient is otherwise benefitting from the study treatment in the opinion of the investigator. Study treatment should be discontinued for a minimum of 3 days before a patient undergoes palliative radiation treatment. Study treatment should be restarted within 28 days as long as any bone marrow toxicity has recovered.

Proprietary Information of MD Anderson

Protocol 2020-1241

19 October 2022

- Concomitant use of herbal preparations containing CYP3A4 inducers (e.g. St John's Wort) is not permitted during the study.
- Grapefruit and grapefruit juice (a CYP3A4 inhibitor) consumption is not permitted during the study.
- **The use of systemic corticosteroids or immunosuppressants after starting the study intervention should be avoided, except:**
 - (1) If a participant is on chronic corticosteroid therapy, e.g. replacement therapy such as physiologic corticosteroid replacement therapy for adrenal or pituitary insufficiency (in dosing not exceeding 10 mg daily of prednisone equivalent) is not considered a form of systemic treatment.
 - (2) Systemic corticosteroids above 10 mg prednisolone or equivalent or other immunosuppressants may be allowed after starting the study intervention for the management of acute conditions (e.g. treatment of non-infectious pneumonitis) or as premedication for radiological contrast infusion as clinically indicated.

Participants may be using inhaled or topical steroids. For more information about steroid use in management of skin toxicities, please refer to **6.3.1.4**.

If treatment with a prohibited medication/therapy is necessary, the patient will be withdrawn from the study after discussion with the sponsor.

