4.1.7 Removal of Patients from the Study

Every effort within the bounds of safety and patient choice should be made to have each patient complete the treatment period of the study. Patients who have treatment discontinued due to PD may be treated with any additional therapy deemed appropriate by the investigator. Patients with disease progression per RECIST can continue on therapy for clinical benefit if deemed appropriate by the investigator.

Patients may be discontinued from the study for any of the following reasons:

- Investigator recommends discontinuation and documents the reason(s)
- There is a need for any treatment not allowed by the protocol
- Patient's decision to withdraw consent or discontinue for any reason
- There is an unacceptable AE thought to be related to study medication

Any patient who discontinues during the treatment period should return to complete safety and disease assessments (see **Appendix A: Schedule of Assessments**).

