6.2 Dose Modification

Any toxicity observed during the study can be managed by interruption of the dose of study treatments or dose reductions. Repeated dose interruptions are allowed as required, for a maximum of 4 weeks on each occasion. Where toxicity recurs following re-challenge with study drugs, and where further dose interruption is considered inadequate for toxicity management, then withdrawal is indicated.

[figure not shown]
If either of the study drugs or both drugs need to be held due to AEs, then the study drug deemed to be responsible for the AE will be held until AE resolves to grade 1 or baseline. When copanlisib or fulvestrant dosing is interrupted, either the patient must recover completely, or the toxicity must revert to NCI CTCAE \leq Grade 1 or baseline before restarting study treatment. Patients whose NCI CTCAE Grade 3 or 4 event does not resolve to \leq 1Grade or baseline within 4 weeks should be withdrawn from the study. When a patient withdraws prior to study completion, all applicable activities scheduled for the final study visit should be performed at the time of withdrawal. Any AEs that are present at the time of withdrawal should be followed until \leq Grade 1 or baseline.

Proprietary Information of MD Anderson

Protocol 2020-1241

19 October 2022

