6.9 Patient Withdrawal/Discontinuation Criteria

Patients may withdraw consent at any time for any reason or be dropped from the study at the discretion of the investigator should any untoward effect occur. In addition, a patient may be withdrawn by the investigator if enrollment into the study is inappropriate, the study plan is violated, or for administrative and/or other safety reasons.

A patient must be discontinued from the study for any of the following reasons:

- The patient or legal representative withdraws consent. Every effort will be made to determine why any subject withdraws from the study prematurely.

A patient must be discontinued from study treatment (but may continue to be monitored in the study) for any of the following reasons:

- The patient or legal representative withdraws consent
- Confirmed radiographic disease progression with the exception of patients who are benefitting from the study treatment in the opinion of the investigator, the patient is clinically asymptomatic, and continuation of study treatment is approved by the sponsor.
- Unacceptable toxicity
- An intercurrent illness that prevents further administration of study treatment
- Investigator's decision to withdraw the patient
- The patient has a confirmed positive serum or urine pregnancy test
- Non-compliance with study treatment or procedure requirements
- Initiation of new anticancer therapy including another investigational agent
- The patient is lost to follow-up. A genuine effort must be made to determine the reason(s) why a patient fails to return for the necessary visits. If the subject is unreachable by telephone, a registered letter, at the minimum, should be sent requesting him/her to contact the clinic
- Death
- Dose interruption that exceeds 4 weeks
- Administrative reasons

When a patient is permanently discontinued from receiving study treatment prior to study completion, all applicable activities scheduled for the final study visit should be performed at the time of withdrawal. The patient will continue to be followed for safety unless consent is withdrawn or the patient is lost to follow-up or initiation of a new anticancer therapy. Patients who discontinue for reasons other than disease progression will have post-treatment follow-up for disease status until PD, death, initiation of new anticancer therapy, withdrawal of consent,

Proprietary Information of MD Anderson

Protocol 2020-1241

19 October 2022

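### Sections 6.2 and 6.4.1 take patients out of the study for events that 6.9 treats as stopping treatment only; read literally, they may end PFS and OS follow-up.

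*Combined protocol and SAP*

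**What the plan says.** Two sections direct removal from the study. Under 6.4.1, if a prohibited therapy becomes necessary, "the patient will be withdrawn from the study after discussion with the sponsor". Under 6.2, patients whose Grade 3 or 4 event has not settled to Grade 1 or baseline "within 4 weeks should be withdrawn from the study". Section 6.2 continues: "When a patient withdraws prior to study completion, all applicable activities scheduled for the final study visit should be performed at the time of withdrawal". It also asks for adverse events to be followed, but does not mention progression or survival.

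Section 4.1.7 is permissive. Its list of reasons for which a patient may leave the study includes "There is a need for any treatment not allowed by the protocol" and an unacceptable drug-related adverse event. It adds: "Any patient who discontinues during the treatment period should return to complete safety and disease assessments".

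Section 6.9 separates leaving the study from stopping treatment:
- "A patient must be discontinued from the study for any of the following reasons": the only item is withdrawal of consent.
- "A patient must be discontinued from study treatment (but may continue to be monitored in the study) for any of the following reasons": the list includes unacceptable toxicity, starting a new anticancer therapy and an interruption longer than 4 weeks.

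Section 6.9 then provides disease follow-up for patients who stop for reasons other than progression, and survival follow-up after progression. Section 4.1.4 sets imaging every 8 weeks until progression, death, new anticancer therapy, withdrawal of consent or loss to follow-up. Section 4.1.5 sets telephone contact every 12 weeks after confirmed progression or new anticancer therapy. Section 3.1 censors PFS and OS at the last follow-up. Section 2.2 makes ORR the Part 2 primary objective, with PFS and OS secondary.

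**The concern.** A patient with a Grade 3 or 4 event unresolved at 4 weeks leaves the study under 6.2 but only stops treatment under 6.9. The follow-up in 4.1.4 is written for patients who discontinue study treatment, and nothing says that it also covers someone withdrawn from the study. If staff apply 6.2 or 6.4.1 to the letter, imaging and survival contact may stop, and the rule in 3.1 would censor the patient at the last contact.

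Toxicity or the need for other treatment may plausibly go with a worse outlook. Censoring at that point would then be informative, and the Kaplan-Meier curves for PFS and OS would lie too high. Follow-up that is not collected at the time may not be recoverable later.

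**Working it through.** **1. The sections side by side**

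| Event | 6.2, 6.4.1, 4.1.7 | 6.9 | Follow-up planned |
|---|---|---|---|
| Grade 3-4 event unresolved at 4 weeks | Leaves the study (6.2) | Closest items, toxicity and interruption over 4 weeks: treatment stops, monitoring may continue | Imaging (4.1.4), later survival calls (4.1.5) |
| Prohibited anticancer therapy | Leaves the study (6.4.1); may leave (4.1.7) | Treatment stops, monitoring may continue | Imaging ends at new therapy (4.1.4); survival calls begin (4.1.5) |
| Prohibited non-anticancer drug | Leaves the study (6.4.1); may leave (4.1.7) | No specific item | Imaging (4.1.4) if classed as stopping treatment |

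**2. Who could be lost**

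For a new anticancer therapy, 6.4.1 changes nothing for PFS, because 4.1.4 ends imaging at that point anyway, and 4.1.5 expressly keeps survival contact. The exposure lies mainly in the first and third rows. Entry to survival follow-up in 4.1.5 is triggered by confirmed progression or new anticancer therapy. A patient with neither reaches it by way of the imaging phase, so losing that phase can lose OS as well as PFS.

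**3. Illustration of size**

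The documents give no figure to reproduce. The visible text has no withdrawal rate, event count or expected median, so every input here is assumed.

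- Exponential event times with an on-study median of 12 months: λ = ln 2 / 12 = 0.0578 per month.
- Gradual withdrawal, with probability w by month 12 in the absence of an event: g = −ln(1 − w) / 12.
- After withdrawal the hazard is h × λ.

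Censoring at withdrawal makes Kaplan-Meier estimate exp(−λt), with a median of 12. The curve for all patients is

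S(t) = exp(−(λ+g)t) + g × [exp(−hλt) − exp(−(λ+g)t)] / (λ + g − hλ).

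Solve S(t_m) = 0.5; the overstatement is 12 / t_m − 1. For w = 10% and h = 2: g = 0.00878, S(12) = 0.486, t_m = 11.54, and 12 / 11.54 − 1 = 4.0%.

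| Withdrawn by month 12 | h = 1 | h = 1.5 | h = 2 | h = 3 |
|---|---|---|---|---|
| 5% | 0% | 1.1% | 2.0% | 3.3% |
| 10% | 0% | 2.2% | 4.0% | 6.6% |
| 20% | 0% | 4.5% | 8.1% | 13.2% |

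The result depends on timing. If instead 10-20% of those at risk all withdraw at month 2, then after month 2 S(t) = (1 − w)exp(−λt) + w × exp(−2λ) × exp(−hλ(t − 2)). With medians of 6 or 12 months, the overstatement is 3.0-7.4% at h = 1.5 and 9.0-22.3% at h = 3. It is again zero at h = 1.

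**The case against.** A reader might infer that the plan ends progression and survival follow-up for these patients, and that PFS and OS are therefore inflated. The documents do not support that. No section says that follow-up ends. Sections 4.1.4, 4.1.5 and 6.9 and the notes to Appendix A provide for it to continue, and 4.1.7 asks patients who discontinue to return for disease assessments.

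The protocol also uses withdrawal loosely. The final-visit instruction in 6.2 recurs in 6.9, where it concerns patients permanently off study treatment. Section 6.2 itself continues adverse-event follow-up after withdrawal. This is a single-center study, and 6.4.1 requires discussion with the sponsor first, so an automatic loss of follow-up is not a given. Section 4.1.7 only permits removal, so it is wrong to say that three sections require it.

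The documents hold no evidence that these patients do worse. Some items in 6.4.1, such as grapefruit and herbal CYP3A4 inducers, have no stated link to prognosis. A response recorded before withdrawal still counts toward ORR. Most of Section 8 and parts of Sections 4 and 6 are not visible, so a censoring rule there cannot be called absent.

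All of this stands, and it reduces the consequence from a fact to a risk. It does not remove the contradiction between 6.2 or 6.4.1 and 6.9. Section 6.9 is not fully firm either: it says that monitoring may continue before saying that disease follow-up will take place, and it opens by letting the investigator drop a patient from the study for untoward effects.

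**Conclusion.** The inconsistency is real and worth correcting. Sections 6.2 and 6.4.1 remove patients from the study, and 4.1.7 permits it, for reasons that 6.9 largely handles by stopping treatment. The consequence is conditional: follow-up may be lost if the wording is applied literally, mainly after toxicity or a prohibited non-anticancer drug.

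If that happens and prognosis after withdrawal is worse, the secondary endpoints PFS and OS are biased upward. The gradual-withdrawal illustration gives roughly 2-13% of the median for 10-20% withdrawn at 1.5-3 times the hazard. Every input is assumed, other timing gives other figures, and equal hazard gives zero, so this is not an estimate for the trial. If follow-up runs as 4.1.4, 4.1.5 and 6.9 describe, this bias does not arise for OS, nor for PFS in toxicity withdrawals who start no new anticancer therapy.

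**What to change.** Reconcile 4.1.7, 6.2 and 6.4.1 with 6.9, so that none of these events ends study follow-up unless consent is withdrawn.

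- In 6.2 and 6.4.1, state that the patient enters disease follow-up under 4.1.4 with its existing stopping points, including new anticancer therapy. Then state that survival follow-up under 4.1.5 runs until death, withdrawal of consent or loss to follow-up.
- In 4.1.7, separate withdrawal of consent from the other items. A blanket replacement of wording would misfit, because consent withdrawal is on the same list.
- In 6.9, make the opening sentence and the monitoring wording agree with this.

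Do not write that imaging continues until consent is withdrawn, since that would contradict the stop at new anticancer therapy in 4.1.4. The clinical criteria for stopping treatment stay unchanged. The cost is a wording amendment; the visits and calls are already planned.

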6.4.2 Potential Drug Interactions

No drug-drug interaction (DDI) effect of copanlisib on fulvestrant metabolism is expected, because copanlisib is not an inhibitor or inducer of drug metabolizing enzymes involved in fulvestrant metabolism, and vice versa.

Proprietary Information of MD Anderson

Protocol 2020-1241

19 October 2022

6.5 Supportive Care

Patients should receive appropriate supportive care measures as deemed necessary by the investigator.

Gastrointestinal Disorders

Nausea, vomiting, and diarrhea have been very common in patients treated with copanlisib. Patients with these side effects may require supportive care, including antiemetics, antidiarrheal medications, and IV fluids. Patients should receive appropriate antiemetic treatment at the first onset of nausea or vomiting in accordance with local practice guidelines. As per international guidance on antiemetic use in cancer patients (European Society for Medical Oncology, National Comprehensive Cancer Network), generally, a single-agent antiemetic should be considered (e.g., dopamine receptor antagonist, antihistamine, or dexamethasone).

Fatigue

Fatigue has been very common in patients treated with copanlisib. Patients with fatigue may require symptomatic management as needed.

Hematological Disorders

Patients with anemia and/or thrombocytopenia may require supportive care, including transfusion of red blood cells and platelets and administration of hematological growth factors.

Metabolism abnormalities

Hypophosphatemia has occurred in patients treated with copanlisib. Phosphate replacement might be needed.

Hyperglycemia

Hyperglycemia has been very common in patients treated with copanlisib. Hydration and/or oral glucose-lowering medication or insulin might be needed depending on the severity of the blood glucose level and the study treatment stage.

Vascular Disorders

Hypertension (includes secondary hypertension) has been frequent in patients treated with copanlisib. Anti-hypertensive treatment might be needed to manage hypertension.

Infections

Lower respiratory tract infections have been very common in patients treated with copanlisib. Infections need to be treated until resolution before resuming the treatment with copanlisib.

6.6 Contraception

Both copanlisib and fulvestrant can cause fetal harm during embryonic development. In pregnant animal models, the administration of copanlisib or fulvestrant caused embryo-fetal death and fetal abnormalities. No information is available on the safety of copanlisib or fulvestrant in pregnant human females. Neither copanlisib nor fulvestrant should be administered to pregnant

Proprietary Information of MD Anderson

Protocol 2020-1241

19 October 2022

women. Female patients of childbearing potential must either abstain from heterosexual intercourse or use a highly effective method of contraception for the course of the study through 150 days after the last dose of copanlisib or fulvestrant. Males with female partners of reproductive potential must abstain from sexual intercourse. Alternatively, they and their partners must use a highly effective method of contraception when engaging in sexual intercourse for the course of the study through 90 days after the last dose of copanlisib or fulvestrant.

Patients should be informed that taking the study medications may involve unknown risks to the fetus (unborn baby) if the pregnancy were to occur during the study. To participate in the study, they must adhere to the contraception requirement for the duration of the study and after the last day of treatment as described in the paragraph above. If there is any question that a patient will not reliably comply with the requirements for contraception, that patient should not be entered into the study.

6.6.1 Female Patients

Women in the following categories are not considered women of childbearing potential:

- Premenopausal female with 1 of the following:
 - Documented tubal ligation
 - Documented hysterectomy
 - Documented bilateral salpingectomy
 - Documented bilateral oophorectomy
- Postmenopausal female
Postmenopausal is defined as ≥45 years of age, with at least 12 months of spontaneous amenorrhea.

Female patients of childbearing potential are eligible to participate if they agree to use a highly effective method of contraception consistently and correctly, as described in **Table 17** during the protocol-defined timeframe.

Table16: Highly Effective Contraception Methods

• Combined (estrogen and progestogen-containing) hormonal contraception
○ Oral○ Intravaginal○ Transdermal

• Progestogen-only hormonal contraception
○ Oral○ Injectable○ Implantable

• Intrauterine devices and intrauterine hormone-releasing system

• Bilateral tubal occlusion (women)

Proprietary Information of MD Anderson

Protocol 2020-1241

19 October 2022

- Vasectomized partner

A vasectomized partner is a highly effective contraception method provided that the partner is the sole male sexual partner of the woman of childbearing potential and the absence of sperm has been confirmed. If not, an additional highly effective method of contraception should be used.

- Sexual abstinence (men and women)

Sexual abstinence is considered a highly effective method only if defined as refraining from heterosexual intercourse during the entire period of risk associated with the study treatment. The reliability of sexual abstinence needs to be evaluated in relation to the duration of the study and the preferred and usual lifestyle of the patient. Periodic abstinence (such as a calendar, symptothermal and post-ovulation methods, withdrawal (coitus interruptus), and the lactational amenorrhea method are not acceptable methods of contraception

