12. Women of childbearing potential must have a negative serum or urine pregnancy test (minimum sensitivity 25 IU/L or equivalent units of human chorionic gonadotropin [HCG]) within 14 days prior to the initiation of treatment and/or postmenopausal women must be amenorrheic for at least 12 months to be considered of non-childbearing potential. Women of childbearing potential (WOCBP) must agree and commit to the use of 2 highly effective methods of birth control throughout the duration of the study until at least 4 months following the last dose of study drug. Acceptable methods are defined as those that result, alone or in combination, in a low failure rate (i.e., less than 1% per year) when used consistently and correctly, such as surgical sterilization, an intrauterine device, or hormonal contraception in combination with a barrier method. Women using systemically acting hormonal contraceptives should add a barrier method. In certain countries (if permitted by law), WOCBP may agree to abide by heterosexual sexual abstinence during the time of participation in this study.
13. Male patients and their female partners of childbearing potential must agree and commit to use a barrier contraception (eg, condom with spermicidal foam/gel/film/cream/suppository) throughout the duration of the study until at least 60 days following the last dose of study drug, in addition to their female partners using either an intrauterine device or hormonal contraception and continuing until at least 4 months following the last dose of study drug. This criterion may be waived for male patients who have had a vasectomy > 6 months before signing the ICF.
14. Willing and able to comply with the protocol for the duration of the study, including undergoing treatment and scheduled visits and examinations.

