- o) Hematology (CBC with platelet and differential WBC count) will be performed at baseline, weekly (D1, D8, D15, D22) during Cycle 1, twice during cycle 2 (D1 and D15), and then at the start of every cycle thereafter (within 3 days prior to treatment), or more frequently if clinically indicated. Finally at EOT/progression.
- p) Clinical chemistry (total protein, albumin, indirect and TB, AST, ALT, ALP, electrolytes [sodium, potassium, calcium, and magnesium], serum phosphate, serum creatinine, creatinine clearance, uric acid, and bile salts) will be performed at baseline, weekly (D1, D8, D15, D22) during Cycle 1, twice during cycle 2 (D1 and D15), and then at the start of every cycle thereafter (within 3 days prior to treatment), or more frequently if clinically indicated. Finally at EOT/progression.
- q) Mandatory blood samples to isolate plasma ctDNA will be collected at pre-treatment (Day -28 to Day 1 of Cycle 1), on-treatment (pre-dose on the same day as the on treatment biopsy on Cycle 2 Day 1, as well as during the first two restaging visits), and post-treatment at EoT. A maximum of 5 ctDNA samples will be collected per patient.
- r) Tumor biopsies, if medically feasible, will be obtained at Screening (within 28 days of Cycle 1 Day 1), on-treatment after fulvestrant and copanlisib administration on Cycle 2 Day 1 and at EOT. Tumor biopsies will be optional but encouraged, especially in patients with a response or prolonged disease control. Tumor biopsies will be used to evaluate genomic biomarkers of response and intrinsic and adaptive resistance, and to evaluate pharmacodynamic markers of engagement.
- s) Pregnancy tests will be only for women with childbearing potential. Only whole blood will be collected for the pregnancy test that will be performed in the Screening period (Day -28 to Day -1).
- t) Additional pregnancy tests will be performed at Day 1 of each Cycle only for women with childbearing potential. Whole blood or urine can be collected for the test.
- u) Pregnancy test for Cycle 1 Day 1 can be skipped if the test for the screening period is performed close to the 1st cycle.

- v) FPG testing will be performed at Screening and before each copanlisib administration on Day 1, Day 8, and Day 15 of each Cycle from Cycle 1 to Cycle 4 inclusive. Starting with Cycle 5, FPG testing will only be performed on Day 1 of each cycle.

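### Tubal ligation both removes and presupposes childbearing potential, and criterion 12's amenorrhea condition is not tied to Section 6.6.1, so pregnancy testing depends on the passage applied

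*Combined protocol and SAP*

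**What the plan says.** Section 6.6.1 opens with a list introduced by "Women in the following categories are not considered women of childbearing potential". One branch covers premenopausal patients with any of four documented procedures. The first of these is "Documented tubal ligation"; the others are hysterectomy, bilateral salpingectomy and bilateral oophorectomy. The other branch is the postmenopausal patient, with the definition: "Postmenopausal is defined as ≥45 years of age, with at least 12 months of spontaneous amenorrhea".

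The section then turns to the remaining women: "Female patients of childbearing potential are eligible to participate if they agree to use a highly effective method of contraception consistently and correctly". It sends them to a table of methods (labelled Table 16, cited in the text as Table 17). One entry in that table is "Bilateral tubal occlusion (women)".

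Criterion 12 appears in Section 5.3 and, with the same wording on these points, in the synopsis. It asks women of childbearing potential for a negative pregnancy test within 14 days before treatment and for two methods of birth control. Its examples of acceptable methods are "such as surgical sterilization, an intrauterine device, or hormonal contraception in combination with a barrier method". On menopause it says "postmenopausal women must be amenorrheic for at least 12 months to be considered of non-childbearing potential". It does not refer to Section 6.6.1.

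Appendix A footnote s states: "Pregnancy tests will be only for women with childbearing potential". Footnote t puts the same limit on the Day 1 test of each cycle, and footnote u lets the Cycle 1 Day 1 test be skipped when the screening test was close to it.

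Section 6.6 says that both drugs are capable of harming the fetus. It cites findings in pregnant animals and reports no information on safety in pregnant women.

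**The concern.** Childbearing potential acts as a switch in this protocol. It decides whether a patient is tested for pregnancy before and during treatment, and whether she must commit to contraception in order to enroll. A switch of this kind needs one setting per patient.

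For tubal ligation the protocol gives two. One passage takes the woman out of the group; two others treat her procedure as something a woman inside the group relies on. For menopause, the eligibility criterion states a condition with fewer elements than the definition in Section 6.6.1 and does not point to that definition. Site staff who apply different passages could handle the same patient differently, and one of those outcomes is that she has no scheduled pregnancy test at all.

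**Working it through.** The plan gives no figure to reproduce here. The check is to set the passages side by side and classify example patients under each.

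**Step 1: tubal ligation.** Assumption: a documented tubal ligation is a form of bilateral tubal occlusion and of surgical sterilization.

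- Under the 6.6.1 list she is not of childbearing potential. By footnotes s and t she has 0 pregnancy tests.
- Under the 6.6.1 table and criterion 12, her procedure is a method used by a woman of childbearing potential. Over *k* cycles she has 1 screening test plus *k* Day 1 tests, so 1 + *k*. If the Cycle 1 test is skipped, the count is 1 + (*k* − 1) = *k*. For *k* = 2 that is 3 tests, or 2 with the skip, against 0.
- Contraception under 6.6 and 6.6.1 is met on either classification, because those sections ask for one highly effective method and the table accepts occlusion. Criterion 12 asks for two methods, so there she would need one more.

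**Step 2: menopause.**

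| Element | Criterion 12 | Section 6.6.1 |
|---|---|---|
| 12 months of amenorrhea | yes | yes |
| Age 45 or over | not stated | required |
| Amenorrhea spontaneous | not stated | required |
| Reference to the other passage | none | none |

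**Step 3: example patients.**

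| Patient | Section 6.6.1 | Criterion 12 read alone |
|---|---|---|
| A. Premenopausal, tubal ligation | exempt by the list; the table treats the procedure as a method for women who are not exempt | not exempt; sterilization is one of her two methods |
| B. Under 45, regarded as postmenopausal, amenorrheic 12 months, none of the listed procedures | not exempt | exempt |
| C. 45 or over, amenorrheic 12 months but not spontaneously, none of the listed procedures | not exempt | exempt if regarded as postmenopausal |
| D. Premenopausal, hysterectomy or bilateral oophorectomy | exempt | no exemption named |

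Patient A is classified in opposite ways whatever reading of menopause is taken. Patients B and C differ only if criterion 12 is applied without the 6.6.1 definition. Patient D shows criterion 12 to be silent rather than contradictory.

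**Step 4: can these patients enroll?** Entry is open from age 18 (criterion 5), and exclusion criterion 3 anticipates earlier chemotherapy and hormonal treatment. Nothing in the criteria rules out A, B or C. The documents give no count or share.

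**The case against.** A reader might infer that the protocol holds two opposed definitions of menopause, and that criterion 12 exempts any woman whose periods have been absent for a year, including through chemotherapy or ovarian suppression. The documents do not support that. Criterion 12 speaks only of postmenopausal women and words amenorrhea as a condition they must meet. The only definition of postmenopausal is the one in 6.6.1. Read together, one passage uses the term and the other defines it. What remains is that criterion 12 states its own condition without pointing to 6.6.1, and it is the text that eligibility staff apply.

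A second objection is that the contraception table defines nothing. It lists methods, and Section 6.6.2 also sends female partners of male patients to it, so the occlusion entry has a use apart from enrolled women. That is fair, and the table should not be called a third definition. But 6.6.1 introduces it for female patients, and criterion 12's mention of surgical sterilization concerns patients directly.

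Third, a reader might infer that a woman with a ligation could go without contraception on one reading. She would not: her procedure satisfies 6.6 either way. The possible second method comes from a separate disagreement over the number of methods (two in criterion 12, one in 6.6 and 6.6.1). For her the consequence is mainly testing.

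Finally, the same passages contain a plainer discrepancy that reaches every woman of childbearing potential: contraception lasts 4 months after the last dose in Section 5.3 but 150 days in the synopsis and Section 6.6. This lowers the rank of the present point but does not remove it.

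**Conclusion.** The text is wrong as written, and the matter is minor. It is an internal inconsistency in an operative safety rule, with no bearing on the response rate, dose-limiting toxicity evaluation or sample size.

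The firm part is tubal ligation, which has two statuses on any reading of the rest, given the assumption that ligation counts as occlusion and as surgical sterilization. Per affected woman, the difference is no pregnancy test against one at screening and one per cycle. The softer part is menopause: the passages can be reconciled by reading 6.6.1 into criterion 12, but nothing in criterion 12 tells the user to do so.

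The number of women affected is unknown. Section 6.6.1 already exempts documented hysterectomy and bilateral oophorectomy, so the documents do not show how many gynecologic patients would be left. Nor should the fetal risk be put more strongly than the protocol puts it: Section 6.6 rests on animal findings and reports no human data.

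**What to change.** Reconcile the passages into one definition of childbearing potential, placed in Section 6.6.1. It should settle whether there is an age limit, whether amenorrhea must be spontaneous, and the single status of tubal ligation and occlusion. Cross-refer to it from criterion 12 in Section 5.3 and in the synopsis, from the contraception table, and from Appendix A footnotes s and t. Correct the table number cited in 6.6.1 and 6.6.2 in the same edit. Which definition applies is for the sponsor's clinical and safety staff to decide; this review does not propose one.

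The cost is wording in those places and, depending on the definition chosen, at most a few more pregnancy tests of the kind already scheduled.
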